#### 15.2.2.1. Severity

Severity will be derived based on the intensity grading:

- Mild: Intensity grade of 1.
- Moderate: Intensity grade of 2.
- Severe: Intensity grade of 3.

In addition, for the intensity it can also be reported as the following:

---

Document: CHAD3-004-EBO-Z\_Interim\_Final\_SAP\_v2\_0  
Author: PPD Version Number: 2.0 Version Date: 14JUN2017

Template No: CS\_TP\_BS016 – Revision 3  
Effective Date: 01May2012

Reference: CS\_WI\_BS005

- Redness:
  - o Unknown. o Uninterpretable.
- Swelling, and fever:
  - o Unknown.

Severity is therefore classed as unknown, uninterpretable, mild, moderate or severe (increasing severity). If there are any missing intensities at the time of the analysis, those will be summarised in the unknown category.

#### 15.2.2.2. Relationship to Study Vaccine

Relationship, as indicated by the Investigator, is classified as not related or related (increasing severity of relationship) and will be obtained from the relationship to study vaccine variable on the Solicited Adverse Events General forms in eSource. Missing relationships should be queried prior to the analysis transfer to Biostatistics. If there are any AEs with a missing relationship to study vaccine at the time of the analysis, an unknown category will be used to summarise those solicited AEs.

### 15.3. SOLICITED AND UNSOLICITED ADVERSE EVENTS (AEs)

The following tables are planned for presentation for the Total Vaccinated Cohort:

- Overview of solicited and unsolicited AEs:
  - o These will be presented together with the overview of unsolicited AEs (refer to Section 15.1.2: All Unsolicited Adverse Events):
    - \*Any AE.
    - \*Any severe (grade 3) AE.
    - \*Any related AE.
    - \*Any severe (grade 3) related AE.
    - \*Any AE leading to premature study withdrawal.
    - \*Any Severe (grade 3) AE leading to premature study withdrawal.
    - \*Any Related AE leading to premature study withdrawal.
    - \*Any Severe (grade 3) AE related leading to premature study withdrawal.
- Solicited and unsolicited AEs experienced by at least 5% of subjects within the 30 day post-vaccination window, including the number of events:
  - o Multiple events are counted as multiple events for the calculation of the number of events (n\*).
  - o AEs will be presented by MedDRA System Organ Class and Preferred Term.
  - o SAEs will be excluded from this table.

### 15.4. LABORATORY EVALUATIONS

Document: CHAD3-004-EBO-Z\_Interim\_Final\_SAP\_v2\_0  
Author: PPD Version Number: 2.0 Version Date: 14JUN2017

Template No: CS\_TP\_BS016 – Revision 3  
Effective Date: 01May2012

Reference: CS\_WI\_BS005

- 

The list of laboratory assessments to be included in the analysis is provided in APPENDIX 5: Laboratory Assessments.

The following listings are planned for presentation based on the Total Randomised Cohort:

- Clinical laboratory results, including change from Baseline and toxicity grading.
- Clinical laboratory results: Platelets, including an indication of subjects with AESIs.
- Malaria rapid diagnosis test (RDT) results.
- Pregnancy test results:
  - o Based on the Total Enrolled Cohort and only includes female subjects with results available.

The following tables are planned for presentation based on the Total Vaccinated Cohort:

- Clinical laboratory results, including change from Baseline:
  - o Descriptive statistics, including the interquartile range.Out of range clinical laboratory results:
  - o Number and percentage (%) of subjects with results above or below the normal range.
  - o Percentage (%) is relative to the number of subjects with result available for the specific test and the relevant time point.
- Toxicity grade shift from Baseline to post-baseline, the table will include the following categories:
  - o Grade 0. o Grade 1. o Grade 2. o Grade 3.
  - o Grade 4.
- Clinical Laboratory Percent Decrease from Baseline to Post-baseline: Platelets ( $10^9/L$ ):
  - o Number and percentage (%) of subjects with decrease in platelets in the derived categories will be summarized.
  - o Decrease in platelets from Baseline will be categorised as follows: Any increase
    - 0 to <10% decrease
    - 10% to <20% decrease
    - $\geq 20\%$  decrease o This table will be repeated for the maximum percent decrease observed between Day 3 and Day 6. o This table will not be repeated as a pooled table.
- Reported pregnancies per most recent vaccination and centre:
  - o The number and percentage (%) of reported pregnancies will be presented per most recent vaccination (Day 0 or Month 6) and centre as well as overall.
  - o The percentage will be based on the number of female subjects of childbearing potential within each centre.

All laboratory tables (unless otherwise noted) will be repeated for the following pooling of results:

---

Document: CHAD3-004-EBO-Z\_Interim\_Final\_SAP\_v2\_0

Author: PPD Version Number: 2.0 Version Date: 14JUN2017

Template No: CS\_TP\_BS016 – Revision 3

Reference: CS\_WI\_BS005

Effective Date: 01May2012

Copyright © 2012 Quintiles Transnational Corp. All rights reserved.

The contents of this document are confidential and proprietary to Quintiles Transnational Corp. Unauthorised use, disclosure or reproduction is strictly prohibited.

- Results following the active ChAd3-EBO-Z vaccination; hence:
  - o EBO-Z/MENACWY-TT subjects: Laboratory results following Day 0 vaccination.
  - o MENACWY-TT/EBO-Z subjects: Laboratory results following Month 6 vaccination.

The following figure is planned for presentation based on the Total Vaccinated Cohort:

- Platelet: Quartile Distribution following Day 0 Vaccination:
  - o Box and whisker plot presenting the platelet distribution up to Day 30. o The mean, median as well as the Q1 and 3 values will be presented on the figure. o The treatment groups will be presented separately on the same figure.

The following laboratory variables, as presented in the planned TLF shells, will be recorded on the Blood Sampling form in eSource:

- Date and time of sample collection:
  - o Haematology samples.
  - o Biochemistry samples.

The following laboratory variables, as presented in the planned TLF shells, will be recorded on the Laboratory Results form in eSource:

- Date of sample collection:
  - o Haematology samples.
  - o Biochemistry samples.
- Result and unit.
- Significance:
  - o Not clinically significant (NCS).
  - o Clinically significant (CS).

The following laboratory variables, as presented in the planned TLF shells, will be recorded on the Malaria RDT and Results form in eSource:

- Date and time of assessment.
- Result:
  - o Positive.
  - o Negative.
- Malaria treatment prescribed per local/national requirements:
  - o Yes.
  - o No.
- Prescribed malaria treatment completed:

---

Document: CHAD3-004-EBO-Z\_Interim\_Final\_SAP\_v2\_0

Author: PPD Version Number: 2.0 Version Date: 14JUN2017

Template No: CS\_TP\_BS016 – Revision 3

Reference: CS\_WI\_BS005

Effective Date: 01May2012

- - o Yes.
  - o No.

The following laboratory variables, as presented in the planned TLF shells, will be recorded on the Pregnancy Test form in eSource:

- Date and time of assessment.
- Result:
  - o Positive.
  - o Negative.

The following pregnancy variables, as presented in the planned TLF shells, will be recorded on the Pregnancy Report form in eSource:

- Date and time of outcome.
- Outcome:
  - o Live infant NO apparent congenital anomaly. o Live infant congenital anomaly. o Elective termination NO apparent congenital anomaly.
  - o Elective termination congenital anomaly.
  - o Spontaneous abortion NO apparent congenital anomaly.
  - o Spontaneous abortion congenital anomaly. o Stillbirth NO apparent congenital anomaly.

---

Document: CHAD3-004-EBO-Z\_Interim\_Final\_SAP\_v2\_0

Author: PPD Version Number: 2.0 Version Date: 14JUN2017

Template No: CS\_TP\_BS016 – Revision 3

Reference: CS\_WI\_BS005

Effective Date: 01May2012

Copyright © 2012 Quintiles Transnational Corp. All rights reserved.

The contents of this document are confidential and proprietary to Quintiles Transnational Corp. Unauthorised use, disclosure or reproduction is strictly prohibited.

- o Stillbirth congenital anomaly. o Ectopic pregnancy. o Molar pregnancy. o Lost to follow-up.
  - o Pregnancy ongoing.
- Relevant family history.

The following laboratory variables, as presented in the planned TLF shells, will be included in the data transfer from Data Management:

- Local laboratory references ranges in reported units.
- Local laboratory reference ranges in SI units.
- Laboratory results in SI units.

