### **11.8. Analysis of safety**

The analysis will be performed on the TVC.

All analyses will be descriptive. Analyses will be performed by age stratum (1 to 5 years, 6 to 12 years, 13 to 17 years) and overall.

In a first step, the safety results will be presented by treatment administered at Day 0 (ChAd3-EBO-Z vaccine [300 subjects] versus *Nimenrix* [300 subjects]). In a second step, all **available** data post-vaccination with the investigational ChAd3-EBO-Z vaccine (ChAd3-EBO-Z vaccine at Day 0 [300 subjects] and ChAd3-EBO-Z vaccine at Month 6 [300 subjects]) will be pooled (600 subjects). The latter aggregated data cannot be presented versus control because of the administration of the investigational ChAd3-EBO-Z vaccine to the children in the Group MENACWY-TT/ EBO-Z, who initially received *Nimenrix* (population overlap).

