#### 2.1.2. PRIMARY ENDPOINTS

- Occurrence of each solicited local and general adverse event (AE), during a 7-day follow-up period after each vaccination (that is, the day of vaccination and 6 subsequent days), in all subjects, in both groups.
- Occurrence of any unsolicited AE, during a 30-day follow-up period after each vaccination (that is, the day of vaccination and 29 subsequent days), in all subjects, in both groups.
- Occurrence of haematological (complete blood count [CBC], including differential count and platelet count) and biochemical (alanine aminotransferase [ALT], creatinine) laboratory abnormalities at Screening, Day 3, Day 6, Day 30, Month 6, Month 6 + 6 days, Month 6 + 30 days and Month 12 in all subjects, in both groups.
- Occurrence of clinical symptoms of thrombocytopenia (AE of specific interest), during a 7-day follow-up period after vaccination at Day 0 (that is, Day 0 up to Day 6), in all subjects, in both groups.
- Occurrence of any serious adverse event (SAE), in all subjects, in both groups.

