#### 15.4.1. DERIVATIONS

Based on the aforementioned variables, the following variables will be derived:

- Relative day:
  - o Calculated relative to Day 0 vaccination (refer to Section 6.1: Reference Start Date and Relative Day).
- Change from Baseline for results in System of International (SI) units (refer to Section 6.7.1: Change from Baseline).
- Derived decrease categories (%):
  - o  $\text{Change from Baseline} / \text{value at Baseline} \times 100$
- Toxicity grade for selected laboratory tests (refer to APPENDIX 6: Laboratory Toxicity Grading for derivation details).
  - o Maximum grade overall will also be derived as the highest post-vaccination toxicity grade across all post-baseline visits and time points.
- Reference range indicator based on the results in SI units.
  - o Low: Result < reference range lower limit.
  - o Normal: Result  $\geq$  reference range lower limit AND result  $\leq$  reference range upper limit. o High: Result > reference range upper limit.

For clinical laboratory results below or above the limit of quantification will be handled as follows:

- Assign as equal to the limit of quantification, for example '<x' will be assigned as x for analysis purposes. SI conversions can be applied to the derived result. In the listings the result will be presented as the SI value (after conversion) with the qualifier symbol concatenated, for example '<y' in SI unit.

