## APPENDIX 5. LABORATORY ASSESSMENTS

Category	Test	Reported Unit	Conversion Factor	SI Unit	Toxicity Grading
Haematology	Basophils	%	1	%	
	Basophils absolute	/mm 	0.001	10  /L	
	Eosinophils	%	1	%	
	Eosinophils absolute	/mm 	0.001	10  /L	
	Haemoglobin	g/dL	10	g/L	Haemoglobin

Document: CHAD3-004-EBO-Z\_Interim\_Final\_SAP\_v2\_0

Author: PPD Version Number: 2.0 Version Date: 14JUN2017

Template No: CS\_TP\_BS016 – Revision 3

Reference: CS\_WI\_BS005

Effective Date: 01May2012

Copyright © 2012 Quintiles Transnational Corp. All rights reserved.

The contents of this document are confidential and proprietary to Quintiles Transnational Corp. Unauthorised use, disclosure or reproduction is strictly prohibited.

	Lymphocytes	%	1	%	
	Lymphocytes absolute	/mm 	0.001	10  /L	
	Mean cell volume	fL	1	fL	
	Monocytes	%	1	%	
	Monocytes absolute	/mm 	0.001	10  /L	
	Neutrophils	%	1	%	
	Neutrophils absolute	/mm 	0.001	10  /L	
	Platelets	/mm 	0.001	10  /L	Platelets
	Red blood cells	/mm 	0.000001	10  /L	
	White blood cells	x10  /μL	0.001	10  /L	White blood cells - decrease
Biochemistry	Alanine aminotransferase	U/L	1	U/L	Alanine aminotransferase increase by factor
	Creatinine	umol/L	1	umol/L	Creatinine
		mg/dL	88.4	umol/L	

Document: CHAD3-004-EBO-Z\_Interim\_Final\_SAP\_v2\_0

Author: PPD Version Number: 2.0 Version Date: 14JUN2017

Template No: CS\_TP\_BS016 – Revision 3

Reference: CS\_WI\_BS005

Effective Date: 01May2012

Copyright © 2012 Quintiles Transnational Corp. All rights reserved.

The contents of this document are confidential and proprietary to Quintiles Transnational Corp. Unauthorised use, disclosure or reproduction is strictly prohibited.

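### For the 12 ungraded laboratory rows, including every differential count, and for high white cell counts, no table in the SAP text counts children newly out of range; the gap matters most in the uncontrolled pooled table

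*SAP*

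**What the plan says.** SAP v2 section 2.1.2 (and protocol 11.1) makes the occurrence of laboratory abnormalities at Screening and at each later sampling visit a primary endpoint. The haematology part is defined as "complete blood count [CBC], including differential count and platelet count".

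SAP v2 section 15.4 plans these laboratory tables on the Total Vaccinated Cohort:

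- Descriptive statistics of values and of change from Baseline.
- An out-of-range table with numerator "Number and percentage (%) of subjects with results above or below the normal range" and denominator: "Percentage (%) is relative to the number of subjects with result available for the specific test and the relevant time point".
- A shift table: "Toxicity grade shift from Baseline to post-baseline, the table will include the following categories", namely Grades 0 to 4.
- A percent-decrease-from-Baseline table, for platelets only.

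The tests analysed are listed in Appendix 5, which has a column showing which of them carry a toxicity grade. The entry for white cells reads "White blood cells - decrease". Section 15.4.1 derives a low/normal/high indicator for each result, but no table crosses that indicator at Baseline with its value at a later visit.

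Unless otherwise noted, the laboratory tables are repeated for results after ChAd3-EBO-Z pooled over both groups (Day 0 in one, Month 6 in the other). Of such pooled data, protocol 11.8 says: "The latter aggregated data cannot be presented versus control". SAP section 6.2 sets Baseline before the first vaccination in both groups.

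**The concern.** For a safety endpoint, the reader wants to know how many children in range before the dose were out of range after it. The by-visit table mixes those children with others who were already out of range. The grade shift separates them, but only for graded tests, and no differential count is graded.

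Numerical eligibility limits (protocol Appendix C, Tables 25 and 27) cover haemoglobin, platelets, total white cells, creatinine and ALT. A child can therefore enter with a differential value outside the local range, unless it is judged clinically significant under section 4.4. An unchanged percentage from Screening to Day 6 may mean that nothing happened, or that new abnormalities were offset by resolved ones. In the pooled table there is no control column to help, so pre-existing and new abnormalities are counted together as post-vaccination findings.

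**Working it through.** **1. Count of rows (SAP v2 Appendix 5, checked against Appendix 6).** 15 haematology + 2 biochemistry = 17 rows.

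- Graded, 5: haemoglobin, platelets, white cells (decrease), ALT, creatinine.
- Ungraded, 17 − 5 = 12: basophils, eosinophils, lymphocytes, monocytes and neutrophils, each as percentage and absolute count (5 × 2 = 10), plus mean cell volume and red cells.

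Counted by parameter, with percentage and absolute merged, this is 7 ungraded of 12.

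**2. What each planned output tells us about the 12 ungraded rows.**

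| Output | Uses the child's own Baseline? | Counts newly out-of-range children? |
|---|---|---|
| Out-of-range table | No | No |
| Grade shift | Not applicable (no grade) | No |
| Platelet percent decrease | Not applicable | No |
| Change from Baseline (mean, quartiles) | Yes | No |
| Subject listing | Yes | Only by case-by-case derivation |

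A rise in white cells above the range is in the same position, because the grade covers decreases only.

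**3. What the totals alone can say.** Take n children measured at both visits, b out of range before the dose and q after it. The number newly out of range lies between max(0, q − b) and min(q, n − b). The documents give no out-of-range rate, so the rates below are assumptions; n = 300 is the planned group size.

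| Before | After | b | q | New cases between | As % of children in range before |
|---|---|---|---|---|---|
| 5% | 5% | 15 | 15 | 0 and 15 | 0 to 5.3 |
| 10% | 10% | 30 | 30 | 0 and 30 | 0 to 11.1 |
| 20% | 20% | 60 | 60 | 0 and 60 | 0 to 25.0 |
| 30% | 30% | 90 | 90 | 0 and 90 | 0 to 42.9 |
| 20% | 25% | 60 | 75 | 15 and 75 | 6.2 to 31.2 |

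**4. The pooled table.** Section 15.4 restricts it to results following the ChAd3-EBO-Z dose. In SAP Table 2, the 0-day pooled time point pairs Day 0 with Month 6, but protocol section 3 and Table 5 schedule no haematology or biochemistry sample at Day 0. The Day 0 group therefore has no scheduled pre-dose laboratory value at that time point. For the Month 6 group, the section 6.2 Baseline lies about 6 months before the dose. A pooled shift needs its own pre-dose reference.

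**5. Illustration of the mixing.** Assume that, of children in range before the dose, 10% become abnormal after ChAd3-EBO-Z and 4% after Nimenrix. Assume also equal resolution in both groups, set so that controls stay at 30% out of range: r = 0.04 × 0.70/0.30 = 0.0933.

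- By-visit table: 0.30 × (1 − 0.0933) + 0.70 × 0.10 = 34.2% against 30.0%. The difference is 4.2 points, SE = √[(0.342 × 0.658 + 0.30 × 0.70)/300] = 3.8 points.
- Newly abnormal among the 300 × 0.70 = 210 in range: 10% against 4%. The difference is 6 points, SE = √[(0.10 × 0.90 + 0.04 × 0.96)/210] = 2.5 points.

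This shows how the two summaries differ under these assumed rates; it is not a power calculation.

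**The case against.** The planned table matches the endpoint and the protocol as written. The endpoint includes Screening, so it reads as prevalence by visit, and protocol 11.8 asks for out-of-range counts, toxicity grading and change from baseline. The SAP delivers all three. A reader might infer that the SAP departs from the protocol or misstates the endpoint; it does neither.

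A reader might also infer that old and new abnormalities cannot be separated at all. That goes too far. Results and change from Baseline are listed by child, and the range indicator is derived. Continuous change uses each child's own Baseline. Under protocol 9.1.4, clinically significant findings, including significant worsening of one present at baseline, are recorded as adverse events and enter those tables if they start within the reporting window. Each source is partial: none counts crossings of the range.

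For Day 0, randomisation balances pre-existing abnormality in expectation, so the difference between groups at Days 3, 6 and 30 is a fair estimate of the net effect. A claim that this comparison is biased would be wrong. It still does not say how many children are newly abnormal, and it does not help the pooled table.

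Three further limits stand. All analyses are descriptive (SAP 7.4), and the illustration assumes equal resolution, which favours the shift; if the vaccine slowed resolution, prevalence would show it and the newly-abnormal percentage would not. Ten of the 12 rows are five cell types listed twice, and platelets, the known signal, are well covered. Finally, SAP section 8 leaves format and content to table shells, which were not available; they might already split by Baseline.

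**Conclusion.** The point holds as a gap in the planned summaries, not as an error or a contradiction between documents. On the SAP text, 12 of 17 laboratory rows, among them all 10 differential-count rows of a primary endpoint, have no Baseline-referenced categorical table. High white cell counts have none either. The number of newly abnormal children can only be bounded: 0 to 60 of 300 at an assumed steady 20%, and wider at higher rates. If few children are out of range at entry, the gap is small (0 to 15 at 5%).

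The weight falls on the pooled post-ChAd3-EBO-Z table, where no control column offsets pre-existing abnormality. The documents do not support reading this as lost power, as bias in the Day 0 comparison, or as evidence of how many children actually enter out of range. The conclusion rests on the SAP text without the table shells. It is a cheap and worthwhile improvement.

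**What to change.** Keep the by-visit out-of-range counts, which the endpoint and protocol 11.8 call for. Add to SAP 15.4 a shift of the derived indicator (low, normal or high before the dose, by low, normal or high at each later visit), at least for the 12 ungraded rows and for high white cells. Report the percentage, with exact 95% CI, of children in range before the dose who become low or high, by group and pooled.

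The reference should be the last sample before the dose concerned: Screening for Day 0, and the Month 6 sample for Month 6. The Month 6 sample should be confirmed as pre-dose from the recorded sampling and vaccination times (SAP 15.4 and 13).

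This needs SAP wording and programming, but no new data. The cost is length. A full version for 17 rows × 7 post-Screening visits × 2 groups × 4 (three age strata and overall) is 952 grids before the pooled repeat, many of them sparse at about 100 children per stratum. Limiting it to 12 rows plus white cells gives 13 × 7 × 2 × 4 = 728. Retaining the full by-visit counts keeps any effect on resolution visible.

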**5.5.2. Intervals between study visit****Table 6 Intervals between study visits**

Interval	Allowed interval
Screening → Visit Day 0	0 to 30 days
Visit Day 0 → Visit Day 3	3 days
Visit Day 0 → Visit Day 6	6 to 8 days
Visit Day 0 → Visit Day 30	30 to 44 days 
Visit Day 0 → Contact Month 3	3 months ± 30 days
Visit Day 0 → Visit Month 6	6 months ± 30 days 
Visit Month 6 → Visit Month 6 + 6 days	6 to 8 days
Visit Month 6 → Visit Month 6 + 30 days	30 to 44 days 
Visit Month 6 → Contact Month 9	3 months ± 30 days
Visit Month 6 → Visit Month 12	6 months ± 30 days 

 Subjects will not be eligible for inclusion in the according-to-protocol cohort for immunogenicity if they make the study visit outside this interval.

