### Pregnancies

The time period for collecting and recording pregnancies will begin at study vaccination and will end at the Month 6 + 30 days visit. See [Section 9.4](#) for instruction on reporting pregnancies.

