### 6.7.2. MOST RECENT VACCINATION

Most recent vaccination prior to assessment/event:

- Calculate the difference in the assessment/start date and all available vaccination dates.
  - o Assessments: Days since vaccination (Day 0/Month 6) = (Assessment date – vaccination date [Day 0/Month 6]).
  - o Events: Days since vaccination (Day 0/Month 6) = (Event start date – vaccination date [Day 0/Month 6]).
- For previous calculation (difference in assess/start date and available vaccination dates), only consider those vaccinations where the days since vaccination is  $\geq 0$  and determine the vaccination (Day 0/Month 6) for which the days since vaccination (as calculated in the previous step) is a minimum.
- Assign the vaccination selected in the previous step (minimum days since vaccination determination) as the most recent.

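### Pregnancy percentages after the Day 0 and Month 6 doses rest on unequal recording periods, so at a constant rate the Month 6 figure would be about one fifth of the Day 0 figure

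*SAP*

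**What the plan says.** SAP version 2.0 added a pregnancy summary to section 15.4. Its content is defined as follows: "The number and percentage (%) of reported pregnancies will be presented per most recent vaccination (Day 0 or Month 6) and centre as well as overall". The denominator is one count per centre: "The percentage will be based on the number of female subjects of childbearing potential within each centre". The table is not limited to girls who received the dose in question, uses no observed time, and has no reporting window of its own. SAP Table 5 (section 15.1.6) sets windows for serious, specific-interest and unsolicited adverse events, but has no row for pregnancies.

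The recording period comes from protocol section 9.3.1: "The time period for collecting and recording pregnancies will begin at study vaccination and will end at the Month 6 + 30 days visit". Protocol Table 5 agrees, since pregnancy recording is not marked at Month 9 or Month 12. The visit intervals are in protocol Table 6: "Visit Day 0 → Visit Month 6 6 months ± 30 days" and "Visit Month 6 → Visit Month 6 + 30 days 30 to 44 days".

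Events are assigned to a dose under SAP section 6.7.2, using the dose with the fewest days before the event: "Assign the vaccination selected in the previous step (minimum days since vaccination determination) as the most recent". Protocol sections 6.6 and 9.2 do not allow a girl who is pregnant at Month 6 to be vaccinated then, although she may stay in the study.

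**The concern.** Two percentages with the same denominator, printed one above the other, invite comparison. Here the upper row collects pregnancies for about half a year and the lower row for about five weeks. A lower figure after the second dose would be expected even if nothing had changed.

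The Month 6 denominator is also not the group at risk for that row. Girls who withdrew before Month 6, or were not vaccinated then, cannot contribute a pregnancy to it but are still counted. Under the assignment rule, a girl not vaccinated at Month 6 keeps Day 0 as her most recent dose, so a pregnancy she reports later falls in the Day 0 row.

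The pooled outputs raise the same problem. Section 15.4 repeats its laboratory tables, unless otherwise noted, for data after ChAd3-EBO-Z: from Day 0 in one group and from Month 6 in the other. The platelet-decrease table is exempted from this; the pregnancy table is not. If the repeat includes it, one percentage would combine about 6 months of recording in half the girls with 30 to 44 days in the other half.

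**Working it through.** The plan gives no expected count, rate or ratio for pregnancies, so there is no figure to reproduce. The check asks what ratio of Month 6 to Day 0 percentage the table would show if the true rate were the same in both periods.

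**Inputs**
- Recording after the Day 0 dose (protocol Table 6): 6 months = 6 × 365.25/12 = 182.6 days, allowed range 152.6 to 212.6.
- Recording after the Month 6 dose (protocol section 9.3.1 and Table 6): 30 to 44 days, midpoint 37.
- Denominator (SAP section 15.4): the same for both rows, so it cancels.
- Pregnancy rate: constant. This is an assumption, not in the documents. It is a reasonable one because the contraception commitment in protocol section 4.3 runs to 30 days after the Month 6 visit.

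**Expected ratio** = days recorded after Month 6 dose / days recorded after Day 0 dose

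| Day 0 window (days) | 30 days | 37 days | 44 days |
|---|---|---|---|
| 152.6 | 0.197 | 0.242 | 0.288 |
| 182.6 | 0.164 | 0.203 | 0.241 |
| 212.6 | 0.141 | 0.174 | 0.207 |

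The central value is 37/182.6 = 0.203, about one fifth. The extremes are 30/212.6 = 0.141 and 44/152.6 = 0.288.

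**Probability scale.** With a 6-month risk p, the risk over d days is 1 − (1 − p)^(d/182.6). For assumed p of 1%, 5% and 10%, the ratio at 37 days is 0.203, 0.207 and 0.211. Over 30 to 44 days it runs from 0.165 to 0.251, so the conclusion does not depend on the level of risk.

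**How much comes from the denominator?** If the Month 6 row were divided only by girls vaccinated at Month 6, the expected ratio would still be 37/182.6 = 0.203. Keeping girls who are no longer at risk in the denominator lowers it further. With 5% of them not at risk (assumed) it is 0.95 × 0.203 = 0.192; with 20% it is 0.80 × 0.203 = 0.162. Recording time dominates, and the shared count adds a smaller bias.

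**Illustration (assumed counts).** Take 100 girls and 10 pregnancies in the first 6 months. The same rate gives 10 × 37/182.6 = 2.0 pregnancies after Month 6 (1.6 at 30 days, 2.4 at 44 days). The table shows 10% beside 2%. Per 100 girl-months the rows agree: 10/(100 × 6) = 1.67 per 100, and 2.03/(100 × 37/30.44) = 1.67 per 100. In a pooled post-ChAd3-EBO-Z table with equal groups, 10% and 2.03% would average to (10 + 2.03)/2 = 6.0%, which describes neither recording period.

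**Influences not quantified.** Protocol Table 5 schedules a pregnancy test at Month 6 but none at Month 6 + 30 days, so only the first window closes with a test; this lowers the Month 6 row. Late reports, or conceptions before Month 6 detected afterwards, would raise it.

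**The case against.** The strongest reply is that the table claims no rate and plans no comparison of Day 0 with Month 6. It gives counts and cumulative percentages, and pregnancy is neither an adverse event in itself (protocol section 9.2) nor an endpoint. Pregnancy test results and outcomes are listed by subject, and pregnancy losses are serious adverse events collected to the end of the study. Numbers will be small. Assume about 100 of the roughly 200 subjects aged 13 to 17 are girls of childbearing potential. With contraception failing in under 1% per year (protocol glossary), that means fewer than 100 × 0.01 × 0.5 = 0.5 pregnancies before Month 6 and about 100 × 0.01 × 37/365.25 = 0.1 after. Real use may give more, but rates split by centre would be very unstable. All of this stands. It limits the importance of the point and argues against rates by centre. It does not make the two percentages comparable.

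A reader might also infer that the table cannot show pregnancies by vaccine. The documents do not establish that. SAP Appendix 1 sets out presentation by treatment group, and group together with visit identifies the vaccine last received. The table shells, which fix the columns, are not available here.

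Nor does the gap favour either vaccine by construction. Allocation is 1:1, so each row contains about half ChAd3-EBO-Z and half Nimenrix recipients, and groups compared within a row have equal windows.

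Finally, the extremes of 0.14 and 0.29 would need all girls to sit at opposite edges of the visit windows. They are outer limits, not a likely range for the group.

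**Conclusion.** The point holds as a minor one. As specified, the Day 0 and Month 6 percentages are not comparable. At a constant pregnancy rate the Month 6 figure is expected to be about one fifth of the Day 0 figure: 0.16 to 0.24 with Month 6 on schedule, and 0.14 to 0.29 at the outer limits. This rests on the constant rate and on sites following the protocol recording period, because the SAP counts reported pregnancies without its own cut-off.

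It is tempting to blame the shared count of girls for the one-fifth ratio. The arithmetic does not support that: a dose-specific count alone leaves the ratio at about one fifth. The shared count is a separate, smaller fault in the Month 6 row. It is also tempting to call the gap a bias in an estimated rate, or to doubt the safety analysis more widely. The documents support neither reading, because no rate is estimated, all analyses are descriptive, and no primary endpoint uses this table. The harm is a safety display that could be misread between rows, and in the pooled post-ChAd3-EBO-Z repeat if that includes this table.

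**What to change.** In SAP section 15.4:

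- Keep the raw counts by visit, by centre and overall.
- Restrict each row's denominator to girls of childbearing potential who received that dose.
- Add pregnancies per 100 girl-months of recording after that dose, by visit and by vaccine last received (ChAd3-EBO-Z or Nimenrix). Count time from the dose to the earliest of the next dose, the end of pregnancy recording, pregnancy or withdrawal. Give these rates overall, not by centre, because counts will be small.
- Footnote the recording period for each row and the date used to assign a pregnancy to a dose, which the SAP does not define for pregnancies.
- State whether the pooled post-ChAd3-EBO-Z repeat includes this table. If it does, show the girl-months contributed by each group.

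The cost is a few lines of SAP text and one recalculated denominator. Vaccination dates, childbearing status and study-conclusion dates are already collected (SAP sections 13, 10 and 9). The downside is that rates from few events will be imprecise, which is why the counts should stay beside them.
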